3.4.5.2. Blinding

The treatments (MC2-01 Cream and MC2-01 Vehicle) will not be blinded to investigative personnel involved in the preparation/application and removal of treatments.

Investigative personnel who are involved in the preparation/application and removal of the treatments will be unblinded and will not perform the evaluation of skin responses. The subjects and the trained evaluator who will be evaluating skin responses will be blinded to IPs and the treatment allocation; however, because of the demarcations/skin coloration remaining on the skin following patch removal, complete blinding of the evaluators cannot be completely assured.

Investigative personnel who are blinded, including the Investigator and trained evaluator involved in the evaluation of responses, will remain blinded during the course of the study until Database Lock and finalization of the Statistical Analysis Plan (SAP).

In the event of an emergency, if possible, the Investigator or designee will contact the Sponsor with notification of the intent to unblind the treatment codes prior to the actual unblinding. If it is not possible to notify the Sponsor prior to the unblinding, the Investigator or designee will contact the Sponsor immediately following the unblinding procedure and follow with a written notification to document the exact manner in which the code was broken and the justification for the unblinding. The Investigator will communicate the treatment identification to only the investigative personnel who require the information to manage the emergency. Unblinding will happen on site at TKL.

3.4.6. Prior and Concomitant Therapy

All medications, including over the counter (OTC) drugs and vitamins, taken within 28 days prior to the start of the study will be recorded at Screening. Thereafter, a record of all medications taken during the course of the study will be made. Information regarding the total daily dose, route of administration, start and discontinuation dates, and indication are to be captured on the subject's CRF.

The following prohibitions will apply for the duration of the study:

- There will be no use of systemic/topical anti-inflammatory analgesics which in the opinion of the investigative personnel will interfere with the study results, including anti-inflammatory medications such as aspirin (81 mg aspirin will be allowed at the discretion of the Investigator), Aleve, Motrin, Advil, or Nuprin for 72 hours prior to and during the study (occasional use of acetaminophen will be permitted);
- There will be no use of systemic/topical corticosteroids within 3 weeks prior to and/or during the study;
- There will be no use of systemic/topical antihistamines 72 hours prior to and during the study;

- There will be no use of medication known to cause phototoxic reactions (e.g., tetracyclines, thiazides, NSAIDs);
- There will be no use of medication which, in the opinion of the Investigator, will interfere with the study results (e.g. anti-inflammatory medications, antipsychotics, anticonvulsants with potential pain relief effects, immunomodulatory medications, and others);
- There will be no use of sunbeds or sunlamps or deliberate exposure of the test sites to natural sunlight or to other sources of UV light;
- There will be no participation in any other clinical study;
- There will be no soaking of test areas; and/or
- There will be no application of any product to the test areas.

The use of or change in the dose of any and all concomitant medication, either prescription or OTC, during the study will be recorded. The reason for use or change of dose of a concomitant therapy may need to be reported as an AE. Therapies (medication and non-medication therapies) not restricted by the protocol may be used. Non-prohibited chronic therapies being used at Baseline may be continued.

All topical or systemic medication listed in the exclusion criteria are prohibited during this study.

See the IB for information about possible drug-drug interactions.⁸

3.4.7. Treatment Compliance

All patches will be applied and removed by investigative personnel. Whereas bathing will be allowed (low tub bath/frontal showers), the patched areas are not to be soaked and are to be kept as dry as possible, per the instructions to be given to each subject. Subjects will be instructed to contact the Investigator before starting any medication, including OTC remedies. In the case of an emergency treatment, the Investigator must be informed as soon as possible. A trained, experienced evaluator will assess study compliance.

Records of patch applications and visit schedule compliance will be recorded on the subjects' CRFs.

If individual patches become dislodged or are misplaced, such that continuous contact with the skin has been interrupted, the subject will be discontinued from further participation in the study.

3.5. Visit Schedule and Assessments

3.5.1. Study Procedures and Visit Schedule

Screening

At Screening, the subjects will receive any necessary written and verbal information, and the informed consent of each subject will be obtained. Demographic data (including Fitzpatrick skin type) will be recorded, a medical history will be taken, and previous and concomitant medications will be reviewed. Eligibility will be determined by review of the inclusion/exclusion criteria.

- Any written and verbal information
- Informed consent
- Demographics
- Previous/concomitant medication
- Review of inclusion and exclusion criteria
- Medical history (including lifestyle and habits)
- Evaluation of application site area

Table 1: Fitzpatrick Skin Types

I	Always burns easily, never tans
II	Always burns easily, tans minimally
III	Burns moderately, tans gradually
IV	Burns minimally, always tans well
V	Rarely burns, tans very well
VI	Never burns, deeply pigmented ^{10, 11}

Day 1

On Day 1, all subjects will be questioned regarding the entry criteria and female subjects of childbearing potential will undergo a UPT. If the subject fulfills all of the inclusion and none of the exclusion criteria, he/she will be allowed participation in the study. Concomitant medications and AEs will be reviewed and recorded at this visit.

Upon enrollment, each subject will be assigned a unique subject number and receive a randomization code, indicating application placement of the study products.

A baseline evaluation of the patch sites will be performed immediately prior to application of the patches to ensure that no conditions, markings, or coloration of the skin will interfere with interpretation of the study results.

A total of 4 application sites (2 cm x 2 cm each) will be planned on each subject's back. Prior to patching, sites will be marked with site numbers. The distance between the patches will be no less than one centimeter. The numbering of the test sites will remain the same throughout the study. The sites will be marked with an indelible, surgical marker.

Minimal Erythema Dose Determination

On Day 1, subjects will have an area of skin on their back, approximately 50 cm², divided into 6 equal sites marked with a surgical marker. The duration of UVA/UVB irradiation for minimal

erythema dose (MED) exposure will be calculated based on subjects' Fitzpatrick Skin Type and the output of the solar simulator. The solar simulator output will be measured prior to each irradiation. Details of the UV irradiation including output of the simulator, time of exposure, equipment used, and staff performing irradiations will be documented. Each of the sites will be irradiated with full spectrum UV light (UVA/UVB), with each exposure differing from the next by a factor of 1.25 (ie, each irradiated site will be exposed to a 25% greater dose of UV irradiation than the previous site).¹²

The areas involved in MED determination will be different from the study product application sites. Evaluation of the exposed sites will be performed on Day 2.¹²

On Day 2, a trained evaluator will examine the 6 irradiated sites and determine the MED for each subject. To determine the MED the sites are read and scored by the trained evaluator for the presence of erythema. There will be a main evaluator for the study; a backup evaluator will also be assigned in the event that an emergency occurs, and the main evaluator is unable to attend the study visit. The lowest exposure dose of the 6 irradiated sub-sites showing an erythema response is selected as the minimal erythema dose (see [Section 3.5.7](#) for scoring scale).

Induction

The Induction Phase consists of a series of 6 patch applications of the study products (twice a week [Monday and Thursday] and subsequent irradiation [Tuesday and Friday] and evaluations of the patch test sites [Thursday and Monday]) over a 3-week Induction Phase.

Under semi-occlusive conditions, 0.2 g of each study product, MC2-01 Cream and MC2-01 Vehicle will be applied to two Webril® patches. The patches will then be applied to their assigned sites on the back for Induction for 24 hours (± 4 hours). This process will be repeated twice each week (Mondays and Thursdays) during the 3-week Induction Phase. The patches will be secured to the skin with airtight nonporous Blenderm® tape. The same study product will be applied to the same test site throughout the Induction Phase.

Application sites will be evaluated immediately prior to study product application.

After 24 hours (± 4 hours) of study product application (eg, Tuesday and Friday), all patches will be removed. The sites will be evaluated using the scoring system detailed in [Section 3.5.7.1](#). One set of patches will be assigned for irradiation and the other will remain non-irradiated, ie, only one application site of each study product will receive irradiation. On all Tuesdays and Fridays, the sites designated for irradiation will be irradiated with 2 times the subject's MED using the full Xenon lamp spectrum.

Adverse events and concomitant medications will be reviewed at each visit and recorded as applicable.

One application/irradiation session may be missed during the Induction Phase. If a subject misses an irradiation session during the Induction Phase, an additional application/irradiation session will be scheduled the Monday of rest period (week 4).

Rest Period (Weeks 4 and 5)

During the Rest Period of approximately 10-17 days, subjects will not receive any application of study materials. An additional application of study product may be applied on the Monday of the

rest period (week 4) if the subject misses an irradiation session during the Induction Phase of the study.

Challenge (Week 6)

On Day 1 of the Challenge Phase, subjects who have completed the Induction Phase and the Rest Period will have study product applications to naïve sites in the same manner as applied during the Induction. As in the Induction Phase, 0.2 g of MC2-01 Cream and MC2-01 Vehicle will each be applied to 4 assigned sites for Challenge for approximately 24 hours (± 4 hours) under semi-occlusive patch conditions. A baseline evaluation of the naïve sites will be performed immediately prior to application of the patches to ensure that no conditions, markings, or coloration of the skin will interfere with interpretation of the study results. The clinical staff will then remove the patches and a trained evaluator will evaluate the test sites. The designated sites and an additional untreated site will be irradiated with 6 J/cm² of UVA (320-400 nm) followed by 0.5 times the MED of UVA/UVB (full-spectrum) irradiation, obtained by using a filtered light source (see [Section 3.5.4](#)). Each site will be evaluated again at approximately 24 hours (± 4 hours), 48 hours (± 4 hours), and 72 hours (± 4 hours) post irradiation.

Adverse events and concomitant medications will be reviewed at each visit and recorded as applicable. A UPT will be performed for female subjects of childbearing potential at the last study visit (if rechallenge is not required).

Rechallenge

A Rechallenge should be performed if a cutaneous response observed during the Challenge Phase indicates possible photosensitization or at the discretion of the Investigator. If it is determined by the Investigator that a Rechallenge should be performed, the Rechallenge patches will be applied as soon as Challenge reactions have resolved. Just as in the Challenge procedure 0.2 g of each study product MC2-01 Cream and MC2-01 Vehicle will each be applied to 4 naïve sites for approximately 24 hours (± 4 hours) using appropriate patches to further discriminate a photosensitization reaction from an irritation reaction. A baseline evaluation of the naïve sites will be performed immediately prior to application of the patches to ensure that no conditions, markings, or coloration of the skin will interfere with interpretation of the study results.

Approximately twenty-four (24) hours (± 4 hours) after study product application, the clinical staff will remove the patches and a trained evaluator will evaluate the test sites. One site of each product and an additional untreated site will be irradiated with full spectrum UV light (UVA/UVB) using a filtered light source. All sites (irradiated and non-irradiated) will be graded for dermal reactions at approximately 24 hours (± 4 hours), 48 hours (± 4 hours), and 72 hours (± 4 hours) following irradiation. Concomitant medications and AEs will also be reviewed. A UPT will be performed for female subjects of childbearing potential at the last study visit.

End of Study

At the EOS, all patches will be removed as described above, and the final evaluations of the test sites will be made.

An EOS examination will be conducted and consist of the following:

- Concomitant medication

- AEs
- UPT in females of childbearing potential

Concomitant medications and AEs will be reviewed and recorded during the whole study. For a detailed listing of scheduled study time points refer to the Visit Schedule and Assessments ([Table 2](#)).

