3.3.3. Interruption or Discontinuation of Treatment

A reaction of at least moderate erythema (2) accompanied with mild, but definite edema (1) to a study product observed after the first patch application/irradiation sequence of the Induction Phase may indicate the subject to be pre-sensitized and may cause the discontinuation of the subject from the study.

After the second reading of the Induction Phase, either of the following conditions will require that the study product be applied to a naïve patch site under open patch conditions:

- Reaction of >50% “p” or “p” with no erythema, mild but definite erythema, moderate or severe erythema; or “D” (see [Table 3](#) and [Table 4](#));
- Any reaction of definite erythema (mild, moderate or severe) with definite edema.

Study product may not be relocated more than twice.

If the reactions noted above occur on an irradiation day during the Induction Phase, the sites will not be able to be irradiated. Patches will be relocated at the subject’s next visit.

The 3 weeks of continuous patch contact during the Induction Phase frequently results in tape-related irritation that is exacerbated by warm weather, but which occurs among some individuals irrespective of the season. Tape-related irritation will not be graded as a photosensitivity response at the patch site but will be noted separately on the case report form (CRF). Severe tape-related irritation will necessitate a change in the application site. As above, the application site will only be changed twice and then the subject must be discontinued.

One application/irradiation session may be missed during the Induction Phase. In case of a missed application/irradiation, an additional application/irradiation during Week 4 must be

performed. In this case, no evaluation will be required following irradiation. Only one missed patch application or irradiation is allowed. A subject must be discontinued and considered not complete if more than one application or irradiation is missed.

In accordance with legal requirements and ICH-GCP guidelines, every subject has the right to refuse further participation in the study at any time and without providing reasons (see also [Section 5.3](#)). A subject's participation is to be terminated immediately upon his/her request. The Investigator should seek to obtain the reason and record this on the CRF.

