3.5.3. Definition of Minimal Erythema Dose

Minimal erythema dose is defined as the length (in time) of light exposure required to produce a minimal erythema reaction 16 - 24 hours after irradiation using a standardized filtered UV light source that emits UVA/UVB (full spectrum) irradiation as part of its emission spectrum.¹²

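### The MED rule requires no unreddened sub-site below the one selected, so if the lowest dose already reddens, the recorded MED is only an upper bound and Induction doses may exceed those intended

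*Protocol*

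**What the plan says.** Under the MED heading of protocol 3.5.1, six sub-sites on the back are irradiated on Day 1, "with each exposure differing from the next by a factor of 1.25". Exposure times are derived from "Fitzpatrick Skin Type and the output of the solar simulator"; no numerical starting dose is given. On Day 2 the evaluator scores the sub-sites for presence of erythema, and "The lowest exposure dose of the 6 irradiated sub-sites showing an erythema response is selected as the minimal erythema dose". Section 3.5.3 defines the MED as the "light exposure required to produce a minimal erythema reaction".

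The recorded MED then sets two later exposures:

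- **Induction:** on every Tuesday and Friday, "the sites designated for irradiation will be irradiated with 2 times the subject's MED using the full Xenon lamp spectrum". There are six sessions. Table 2 puts the first on Day 2, the day the MED is read.
- **Challenge:** a fixed 6 J/cm² of UVA, "followed by 0.5 times the MED of UVA/UVB (full-spectrum) irradiation".

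Neither document says what to do if the lowest dose already reddens or if no dose does. The SAP only lists the six readings and the resulting MED (Listing 16.2.5).

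**The concern.** A graded series locates a threshold only if it has a negative reading below the first positive one. The selection rule does not ask for that negative. For sub-sites 2 to 6 it follows from the word lowest. For sub-site 1 nothing lies below, so the true MED may equal D1 or be an unknown distance under it. The series then cannot show that D1 gives the minimal reaction that 3.5.3 calls for, yet the rule records D1 and the plan doubles it.

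Those exposed are healthy volunteers with Fitzpatrick types I to III, who have no therapeutic benefit to set against avoidable UV. The evaluator holds the warning on Day 2, before the first Induction dose, but the protocol attaches no action to it. At the other end of the series, if no sub-site reddens, there is no MED to multiply.

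**Working it through.** The plan states no limit on the true-MED multiple, so there is no figure of its own to reproduce. Its description of the step is consistent: a factor of 1.25 is a 25% increase.

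**Inputs.** Step 1.25, six sub-sites, 2 × MED over six sessions, and 0.5 × MED at Challenge (all 3.5.1). Call the lowest dose D1. Let k be the number of steps by which the true MED lies below D1. The documents do not give k, so it is an assumption, shown here from 0 to 3.

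**Step 1: bracketed series.** If sub-site j (2 to 6) is the lowest to redden, sub-site j−1 did not. The true MED therefore lies above D_j/1.25 and at or below D_j. Nominal 2 × MED divided by the true MED runs from 2.0 to under 2 × 1.25 = 2.5. This is ordinary grid error.

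**Step 2: lowest dose reddens.** With rising doses this is the case where all six redden. The only constraint is that the true MED is at or below D1. With true MED = D1/1.25^k, an Induction session delivers 2 × 1.25^k and the MED-based part of Challenge delivers 0.5 × 1.25^k.

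| k (assumed) | 1.25^k | Per Induction session (× true MED) | Six sessions, at most | MED-based Challenge dose (× true MED) |
|---|---|---|---|---|
| 0 | 1.000 | 2.0 | 12.0 | 0.50 |
| 1 | 1.250 | 2.5 | 15.0 | 0.63 |
| 2 | 1.563 | 3.1 | 18.8 | 0.78 |
| 3 | 1.953 | 3.9 | 23.4 | 0.98 |

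The six-session column is 6 × the unrounded session multiple. It is a maximum, because 3.3.3 may stop some irradiations. Only k above 1 takes a session beyond the bracketed range.

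**Step 3: comparison with what the series itself delivers.** Sub-site 6 receives 1.25^5 = 3.05 × D1 on Day 1. One Induction session at 2 × D1 is 2/3.05 = 0.66 of that, about one third lower. The areas are similar: 50/6 = 8.3 cm² for a sub-site, against 2 × 4 = 8 cm² for the two irradiated product sites. At k = 2, sub-site 6 has received 3.05 × 1.5625 = 4.8 times the true MED, against 3.1 in an Induction session. The difference is repetition: one exposure at sub-site 6, up to six at the product sites.

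**Step 4: Challenge.** The MED-based dose reaches one true MED only when 0.5 × 1.25^k = 1, that is k = ln 2 / ln 1.25 = 3.1 steps. Irradiated cream, irradiated vehicle and the untreated irradiated site all receive the same dose.

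**Step 5: do existing rules act in time?** Section 3.3.3 provides that after certain reactions "the sites will not be able to be irradiated". That rule starts after the second Induction reading (Day 4), while the first 2 × MED dose is given on Day 2. It responds to a reaction at the product site, and the MED result does not trigger it.

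**The case against.** The case for leaving the text alone has several good parts.

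- **Other provisions can stop the dose.** A reader might infer that the Investigator's general power to withdraw a subject is the only stop. It is not. Section 5.5.1 says approval requirements must not hold up immediate action for subject safety, so a dose can be withheld without withdrawing anyone. Section 3.3.3 also makes withdrawal mandatory when a subject develops a condition that would have failed the safety-related exclusions. A markedly exaggerated UV response arguably falls under exclusion 1 or 18, though not every all-red series would. This stands. What remains missing is a step tied to the MED reading.
- **An all-red series is made less likely.** Skin type and measured lamp output set the exposures, and exclusions 1, 6, 12 and 18 remove many sensitive subjects. This also stands, but none of it checks the result once the series is read.
- **The per-session excess is modest.** Step 3 shows that each dose is below one already given. This stands for a single session and does not settle the repeated exposure.
- **A rule may sit elsewhere.** The MED procedure cites an external reference, and the site's standard operating procedures bind the study. Neither can be seen here. If a rule exists there, the protocol should point to it.
- **A mandatory repeat series would be too much.** This is right: it adds UV to a possibly sensitive volunteer and uses the only permitted missed session.

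**Conclusion.** The gap is real and narrow. Followed exactly, 3.5.1 can record as the MED a dose that is only an upper bound, and then double it on the same day. For an assumed k of 0 to 3, an Induction session delivers 2.0, 2.5, 3.1 or 3.9 times the true MED, against 2.0 to under 2.5 for a bracketed series. It should be corrected for the volunteers' sake. Neither k nor the frequency of an all-red series can be taken from the documents, and the bounds ignore reading and lamp error.

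Three stronger readings are not supported:

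- **That 2.5 is a protocol safety limit being breached.** It follows from the 1.25 grid. The documents set no such limit.
- **That the photosensitization result is compromised.** Through k = 3 the MED-based Challenge dose stays below one true MED, and the irradiated control sites share it. The effect on the diagnosis is small, and no loss of subjects from Population I follows from the gap itself.
- **That totals of 18.8 or 23.4 MED would be reached.** They are maxima under an assumed k, and 3.3.3 may stop irradiations first.

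**What to change.** Add to 3.5.1, with a cross-reference in 3.3.3:

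> Induction irradiation proceeds only if the selected MED sub-site shows erythema and at least one lower sub-site shows none. Otherwise the subject is not irradiated, is discontinued and replaced, and is kept in Population III only.

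This covers both ends of the series and changes no UV multiple. It needs no new data, because Listing 16.2.5 already holds the six readings. Population III is the right home because product is applied on Day 1, before the MED is read. Replacement fits the 3.3.1 commitment to enrol enough subjects for 50 evaluable completers.

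The cost is an occasional replaced subject, including some whose true MED is at D1 or within one step of it and who would have received no more than the ordinary multiple.

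If the sponsor prefers to retain such subjects, one repeat series is an option and is not required. It would be given on fresh skin on Day 4 and read on Day 5 before irradiation, with the withheld session made up on Days 22 and 23. That leaves 36 − 23 = 13 days to Challenge, within the 10 to 17 allowed. After an all-red series the repeat would run from D1/1.25^5 up to D1, which brackets any k below 5. Its price is about 50 cm² more irradiated skin, a seventh application and the one permitted miss. Post-UV readings at that subject's irradiated sites also fall from 10 to 8 of 11, which pulls the irradiated versus non-irradiated contrast toward zero. SAP 11.2.2 would have to count the make-up as a scheduled session.
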